8 STUDY ASSESSMENTS AND PROCEDURES

A table of study procedures and activities is presented in Section 1.2.

8.1 Screening Process

Before conducting any study-related activities, the ICF must be signed and dated by the subject or their legally authorized guardian and retained by the site and the subject (Section 10.1.1). Evaluation of the entrance criteria are performed during the screening process.

8.1.1 Demographics and Baseline Characteristics

The subject's demographic data will be recorded.

8.1.2 Medical History

During Screening, medical history, and concomitant mediations will be documented.

8.1.3 Physical examination

A physical examination will be conducted during Screening. Any relevant clinically significant abnormalities noted prior to enrollment should be recorded in the eCRF as part of the medical history (and not as an AE).

8.1.4 Respiratory Support Parameters

During screening, information on respiratory support parameters will be captured for subjects receiving MV. For the initial intubation, the following must be documented:

- Date and time support started;
- The type of respiratory support and mode.

Lung compliance should be recorded during screening.

8.1.5 Enrollment

Eligible patients will be enrolled into the study and receive lucinactant treatment. Treatment initiation is to begin within 6 hours of enrollment. The time of enrollment is defined as the time at which it has been confirmed that the subject has met all inclusion criteria and has not met any

exclusion criteria, and a request to the pharmacy to prepare study drug has been made. Enrollment should occur within 7 days of endotracheal intubation and MV.

Following enrollment, dosing will proceed once the reconstituted product has been prepared (see the Study Manual for reconstitution and preparation instructions). Treatment initiation is to begin within 6 hours of enrollment.

Just prior to dosing, vital signs (including blood pressure, mean airway pressure, weight, and body temperature) will be assessed.

8.2 Treatment Period

Reconstituted lyophilized lucinactant is administered as a liquid within 7 days of initial intubation.

8.2.1 Gas Exchange Parameters and Arterial Blood Gases

Values for fraction of inspired oxygen (FiO₂), oxygenation from pulse oximetry (SpO₂), mean airway pressure (P_{aw}), end-tidal CO₂ (EtCO₂), and arterial blood gases (ABGs; PaO₂, PaCO₂, pH) will be recorded from just prior to dose administration and at 1 (\pm 0.25), 2 (\pm 0.25), 4 (\pm 0.5), 8 (\pm 0.5), 12 (\pm 1.0), 18 (\pm 1.0), and 24 (\pm 1.0) hours after dose administration, daily through Day 5, and at Day 30.

P/F and S/F ratios will be determined.

8.2.2 Vital signs

Blood pressure, heart rate, and body temperature will be measured every 12 ± 1.0 hours until Day 5 and at Day 30. Systolic and diastolic blood pressure should be measured using either an arterial line or a manual sphygmomanometer with the patient in a supine or semi-supine position.

Weight will be measured at baseline and at Day 30.

8.2.3 Respiratory Support Parameters

Information on respiratory support parameters will be captured through Day 30 or discharge, whichever occurs first. For each intubation and change in respiratory support, the following must be documented:

• Date and time

- The type of respiratory support and mode
- The reason for each intubation and change of respiratory support

Lung compliance should be recorded every $12 (\pm 1.0)$ hours through Day 5. The plateau pressure and peak inspiratory pressure (PIP) will be measured every $12 (\pm 1.0)$ hours through Day 5. The ventilation index will be calculated.

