- Safety and Tolerability of reconstituted lyophilized lucinactant given as a bolus to patients with COVID-19.
- Change from baseline in OI at 12 hours post initiation of dosing. OI is defined as P_{aw}×FiO₂×100/PaO₂.

Secondary Efficacy Variables:

- Change from baseline through 24 hours post dosing initiation:
 - \circ FiO_{2:}
 - o PaO₂;
 - o SpO₂;
 - o OI;
 - o PaCO₂;
 - o ETCO₂;
 - P/F and or S/F ratios, defined as PaO₂ or SpO₂ divided by FiO₂;
 - Plateau pressure and peak inspiratory pressure (PIP) measured on the ventilator;
 - Ventilation Index (VI). VI is defined as $[RR \times (PIP PEEP) \times PaCO_2]/1000$;
 - o Lung compliance;
 - o Pressure-volume loops if ventilator technology permits.
- Through 30 days:
 - o Daily lung compliance (static) on ventilator;
 - Ventilator-free days;
 - o Days in the intensive care unit (ICU);
 - Days in the hospital;
 - o Incidence of all-cause mortality;
 - o Organ failure free days.

Safety Variables:

- All-cause mortality;
- Peri-dosing adverse events (desaturation, bradycardia, ET reflux, hypotension)
- AEs and serious AEs (SAEs). SAEs that are ongoing at Day 30 will be followed for an additional 30 days;
- Air leaks as AEs of special interest;
- Assessments of vital signs.

Study Population:

The study population will be comprised of adults 18-75 (inclusive) who are positive for SARS-CoV-2, are exhibiting symptoms of severe COVID-19 infection, who are intubated and are receiving mechanical ventilation in a critical care environment.

The objective of the pilot safety study is to evaluate the safety and feasibility of lucinactant administration in COVID-19 patients. A small number of patients should be sufficient to provide evidence that liquid lucinactant can be safely delivered as an intratracheal bolus. A total of up to 30 study subjects will be enrolled (see "Treatment Group" section).

Description of Sites:

Approximately 15 study sites in the United States and Argentina.

Description of Study Intervention:

Reconstituted lyophilized lucinactant will be given at a dose of 160 ml (30 mg TPL/ml), delivered as a liquid in the trachea through the endotracheal tube. Lyophilized lucinactant has the following four active ingredients:

- sinapultide (a synthetic peptide), consisting of amino acid residues lysine (K) and leucine (L), according to the sequence KLLLKLLLKLLLKLLLKKLLLK (KL₄);
- dipalmitoyl-phosphatidylcholine (DPPC);
- palmitoyloleoyl-phosphatidylglycerol, sodium salt (POPG, Na); and

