7.3 Lost to Follow-Up

All efforts should be undertaken to ensure that no subject is lost to follow-up. It is expected that subjects will remain in the study site until the end of study; however, if a subject is discharged prior to the final evaluation, the subject should be contacted for the Day 30 visit. If the subject cannot be reached, at least 3 additional attempts must be made (at least one contact using telephone and at least one using email). If the subject still cannot be reached, a certified letter should be sent to the subject. If contact cannot be re-established after the certified letter, the subject will be considered lost to follow-up.

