8.2.5 Readmissions and death

Readmissions and death will be reported through discharge and Day 30. Hospitalization will be defined as any unplanned hospitalization (including admission to a hospital or any attendance in an acute care setting e.g. ED, or in another health care facility) of 24 hours or greater, regardless of whether the patient was admitted to the hospital.

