8.3 Safety and Other Assessments

8.3.1.1 Concomitant Medications

Concomitant medications and therapies required for the general care of the subject are permitted, including remdesivir and off-label drugs. Other investigational agents or investigational medical devices should be avoided. Concomitant medications will be documented until the time the subject completes the Day 30, is discharged from the hospital, dies, or is transferred to another hospital. Dose, route, unit, frequency of administration, indication for administration, and dates of medication will be captured on the CRF.

8.3.1.2 *Tolerability of drug administration*

During dosing, the incidence of the following will be recorded:

- Oxygen desaturation
- Bradycardia
- Hypotension
- ET tube obstruction

In addition, information on (time, reason) and the incidence of dosing interruptions or dosing discontinuations will be collected.

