9.4.3.2 Through 30 Days

Daily lung compliance on ventilator, ventilator free days, days in the ICU, days in the hospital, organ failure free days, and all-cause mortality will be summarized as was done for the primary endpoint.

All deaths will be summarized using frequency and percent, overall and by type of death (respiratory or not respiratory) and included as part of the assessment of safety. Also, the deaths will be listed by subject and narratives for each death will be included. In this study, the secondary endpoint of ventilator-free days (VFD) is a mortality adjusted assessment. This issue will be dealt with in more detail in preparation for the next study.

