### **5.4.3 Respiratory Support and Supplemental Oxygen**

The respiratory support includes mechanical ventilation and extracorporeal membrane oxygenation (ECMO). Information on respiratory support parameters will be captured from screening through Day 30 or discharge, whichever occurs first. For each intubation and change in respiratory support, date and time, the type of respiratory support and mode, the reason for each intubation and change of respiratory support will be documented.

Lung compliance should be recorded every 12 ( $\pm 1.0$ ) hours through Day 5. The plateau pressure and peak inspiratory pressure (PIP) will be measured every 12 ( $\pm 1.0$ ) hours through Day 5. The ventilation index will be calculated.

The number of subjects requiring respiratory support in the delivery room, including sustained inflation, will be summarized using frequency and percent.

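### The dated ventilator record stops at discharge, but ventilator-free days run to Day 30, so the count cannot be derived correctly for subjects who leave ventilated or are reintubated later

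*Protocol*

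**What the plan says.** The Protocol 1.1 Summary lists "Ventilator-free days" among the outcomes through 30 days. SAP 1.2.3 does the same. The data behind it are the dated entries for each intubation and change of support, and Protocol 8.2.3 limits these: "Information on respiratory support parameters will be captured through Day 30 or discharge, whichever occurs first". SAP 5.4.3 has the same limit: "captured from screening through Day 30 or discharge, whichever occurs first".

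The SAP Executive Summary, under Study Duration, goes further. It follows subjects for safety and efficacy until discharge, transfer or death, and puts the final visit at discharge or transfer if that precedes Day 30.

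Other places continue past discharge:
- Protocol 8.2.5: "Readmissions and death will be reported through discharge and Day 30".
- Protocol 7.3: "if a subject is discharged prior to the final evaluation, the subject should be contacted for the Day 30 visit".
- Protocol 8.4.5 assesses adverse events through Day 30.
- The schedule in Protocol 1.2 marks respiratory support parameters in the Day 6 to 30 period and sets the final visit at Day 30, withdrawal or death.
- SAP 5.5 lists respiratory support parameters at the Day 30 visit.
- SAP 1.2.2 follows efficacy until the subject completes or withdraws.

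On counting, Protocol 9.4.3.2 says only that "the secondary endpoint of ventilator-free days (VFD) is a mortality adjusted assessment" and leaves the detail to the next study. SAP 4.3 allows no imputation and uses available data only.

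**The concern.** The window for the endpoint is longer than the window for the data it needs. A subject who leaves the site on a ventilator, or goes home and is reintubated before Day 30, has no required ventilation dates after leaving. The plan itself provides for early discharge (Protocol 7.3), readmission (8.2.5) and transfer (8.3.1.1 and the SAP Executive Summary).

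With one arm and no hypothesis test, the descriptive summary is the result. SAP 1.2 also says that the efficacy estimate will be used to size future studies, although it does not say which endpoint is meant. If the handling of unrecorded days is left to whoever programs the table, the same data can give materially different means.

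**Working it through.** The documents give no expected value for ventilator-free days and no derivation, so there is no planned figure to reproduce. The check has two parts.

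**1. Do the other sources fill the gap?**
- Readmission reports show that a subject returned to hospital, not the days of ventilation.
- Adverse event records carry onset and resolution of the event, which need not match the start and stop of ventilation.
- Respiratory support at Day 30 is one status point. It cannot date what happened between leaving and Day 30. Under the SAP Executive Summary even that point is lost, because the final visit moves to discharge or transfer.
- The mortality adjustment concerns death, not survivors with unrecorded days.

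So partial information exists, but no required dated record.

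**2. What would different counting rules give?**
Inputs: a 30-day horizon (from the endpoint), N = 30 (Protocol 9.2, upper limit) and N = 20 (SAP 2.2.3). The subjects below are assumed. All are ventilated from Day 1, and the count is simply days off the ventilator. The documents do not say whether days before a reintubation count.

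| Assumed subject | True count | Unrecorded days count as free | Recorded days only |
|---|---|---|---|
| A: leaves ventilated at end of Day 15, weaned at end of Day 28 | 30 − 28 = 2 | 30 − 15 = 15 (error +13) | 0 (error −2) |
| B: ventilated Days 1–10, discharged at end of Day 20, reintubated Days 23–27 | 30 − 10 − 5 = 15 | 30 − 10 = 20 (error +5) | 20 − 10 = 10 (error −5) |
| C: ventilated Days 1–10, discharged at end of Day 20, never reintubated | 30 − 10 = 20 | 20 (error 0) | 20 − 10 = 10 (error −10) |

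If unrecorded days count as free, k subjects of type A shift the mean by 13k/N:

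| k | N = 30 | N = 20 |
|---|---|---|
| 1 | 0.43 | 0.65 |
| 3 | 1.30 | 1.95 |
| 6 | 2.60 | 3.90 |

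Each type B subject adds 5/30 = 0.17 or 5/20 = 0.25 day.

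If only recorded days count, a share s of type C subjects shifts the mean by −10s. With s = 0.5 (assumed) the mean is 5 days too low at either N.

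A third reading sets the value to missing for subjects with unrecorded days. Dropping subject A, whose true count is 2, raises the mean whenever the remaining subjects average more than 2.

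**The case against.** A reader might infer several stronger claims that the documents do not support.

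- *Ventilator-free days are overstated.* This follows only if unrecorded days are counted as free, or if low-count subjects drop out. The available-data rule in SAP 4.3 equally allows a count of recorded days only, which understates the endpoint for everyone discharged well. The direction is undetermined.
- *There are no ventilator data after discharge.* This is too strong. A reintubation on readmission would normally surface as a serious adverse event, and the Day 30 contact gives a status. What is missing is a requirement for dates.
- *Protocol 8.2.3 ends capture at transfer.* It says discharge only, and Protocol 8.3.1.1 treats the two as separate events: "is discharged from the hospital, dies, or is transferred to another hospital". The transfer cut-off comes from the SAP Executive Summary, so subject A is lost only under that text or if a site treats transfer as discharge.
- *The error can be judged against the 3.8-day difference in the sponsor's earlier ARDS trial (14.4 and 10.6 days, Protocol 2.3).* Both figures are lucinactant groups, over 28 days. Standard of care was 13.9. This is not a drug-versus-control yardstick.
- *The error favours the drug.* There is no comparator, and the direction is open.

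It is also fair to say that Protocol 7.3 expects subjects to remain at the site to the end of the study, so few may be affected, and that no primary endpoint, test or power calculation is involved. These arguments limit the size and direction of the problem. They do not remove the mismatch between the two windows.

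**Conclusion.** The point holds in limited form. As written, the plan stops the dated ventilation record at discharge while the endpoint runs to Day 30, and it gives no rule for the days in between. Ventilator-free days therefore cannot be derived correctly for subjects who leave ventilated or are reintubated after leaving. Subjects who leave well are also exposed to an arbitrary choice of counting rule.

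The size rests on assumptions: the subject histories are invented for illustration, and the documents give no transfer, early-discharge or readmission rate. Because the endpoint is secondary and descriptive, the change is worth making but is not critical. It is best made before enrolment ends, since dates not collected during the trial may be hard to recover.

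**What to change.** 1. In Protocol 8.2.3 and SAP 5.4.3, change the capture window to *through Day 30, death or withdrawal of consent, whichever occurs first*. The withdrawal limit respects the rule in Protocol 1.1 that data collection ends when consent is withdrawn.
2. Reconcile Protocol 8.2.3, SAP 5.4.3 and the SAP Executive Summary with Protocol 1.2 and 7.3 and SAP 1.2.2 and 5.5, so that discharge or transfer does not end follow-up in one place and continue it in another.
3. At the Day 30 contact already planned, for anyone who has left the site, record discharge destination, ventilation status on leaving, and start and stop dates of any later invasive ventilation or ECMO. ECMO belongs here because its duration is listed as an endpoint in Protocol 3.
4. In the SAP, state that days ventilated elsewhere count as ventilated, and that days after leaving off the ventilator with no reported reintubation count as free. Report subjects who left ventilated with unknown later status separately, with a best-case and worst-case range, as a stated exception to SAP 4.3. For one who left at the end of Day 15 the range is 0 to 15 days, which is 15/30 = 0.50 day on the mean at N = 30 or 15/20 = 0.75 at N = 20. The same paragraph should say how death and days before a reintubation are counted.

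Cost: wording changes in both documents, a few questions at an existing contact, and occasional calls to receiving facilities. A reintubation elsewhere that nobody reports would still be missed. No treatment or visit changes.

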8.2.4 Pressure Volume Loops

Pressure volume loops will be recorded every 2 (± 0.25) hours through 24 hours.

8.2.5 Readmissions and death

Readmissions and death will be reported through discharge and Day 30. Hospitalization will be defined as any unplanned hospitalization (including admission to a hospital or any attendance in an acute care setting e.g. ED, or in another health care facility) of 24 hours or greater, regardless of whether the patient was admitted to the hospital.

8.3 Safety and Other Assessments

8.3.1.1 Concomitant Medications

Concomitant medications and therapies required for the general care of the subject are permitted, including remdesivir and off-label drugs. Other investigational agents or investigational medical devices should be avoided. Concomitant medications will be documented until the time the subject completes the Day 30, is discharged from the hospital, dies, or is transferred to another hospital. Dose, route, unit, frequency of administration, indication for administration, and dates of medication will be captured on the CRF.

8.3.1.2 *Tolerability of drug administration*

During dosing, the incidence of the following will be recorded:

- Oxygen desaturation
- Bradycardia
- Hypotension
- ET tube obstruction

In addition, information on (time, reason) and the incidence of dosing interruptions or dosing discontinuations will be collected.

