2.4 Risk/Benefit Assessment

2.4.1 Known Potential Risks

Risks for this study must be considered within the context of treating adults with COVID-19, which carries with it substantial risk of morbidity and mortality. Intratracheal instillation of surfactant into the lung requires endotracheal intubation, often with concomitant positive pressure MV. However, patients in this trial will have been intubated to treat their underlying condition. MV is associated with morbidities such as ventilator-associated lung injury and volutrauma/barotrauma resulting in air leak syndromes such as pneumothorax and/or pulmonary interstitial emphysema (PIE). Surfactant instilled intratracheally has been associated with peridosing events such as transient hypoxemia, bradycardia, and hypotension. These are usually not severe, are transient, and typically resolve within 30 minutes.

Studies in adults with ARDS administered lucinactant using bronchopulmonary surfactant lavage of each segment of the lungs to attempt to remove alveolar debris and effectively deposit functional surfactant. Safety results show that this procedure was generally safe and well tolerated; however, this procedure was more invasive than other delivery methods and required more time and skill to complete dosing and may have contributed to the increased treatment-emergent AE in the lucinactant-treated subjects. A total of 44 of 110 lucinactant patients (40%) and 14 of 42 standard of care patients (33%) experienced an SAE. A total of 15 of 88 lucinactant patients (17%) in KL4-ARDS-04 had an SAE that was considered to be related to study treatment (patients receiving

standard of care had all AEs and SAEs defined as not study-treatment related). A total of 28 deaths were observed in the ARDS studies. In the KL4-ARDS-04 Study, all-cause mortality at the end of Day 28 was numerically, but not statistically significantly, higher in lucinactant Group B.2 (24%) compared with lucinactant Group B.1 and SOC (14% in each).

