6.1.2 Dosing and Administration

Eligible patients will be enrolled into the study and receive lucinactant treatment. Treatment initiation is to begin within 6 hours of enrollment. The time of enrollment is defined as the time at which it has been confirmed that the subject has met all inclusion criteria and has not met any exclusion criteria, and a request to the pharmacy to prepare study drug has been made. Enrollment should occur within 7 days of endotracheal intubation and MV.

Initial Dose

Reconstituted lyophilized lucinactant is administered using the following instillation procedure:

- a. The ventilator will be set at an FiO₂ of 1.00.
- b. To prevent cough and throat closure, the patient may receive a short-acting paralytic.
- c. Lucinactant will be administered via a number 10 French end-hole suction catheter positioned in the trachea at the end of the endotracheal tube. The suction catheter will be inserted into the ventilator's inspiratory tubing via a side-port connector.
- d. The total dose of lucinactant will be divided into four quarter-doses (40 ml). Each quarter-dose will be further sub-divided into aliquots of 20 ml. Each quarter-dose will be instilled in one of the four positions listed below, one aliquot at a time. After each quarter dose, ensure the patient is stable before continuing the dosing.

- 1. Quarter-dose administered with the patient supine and positioned 45° to the right. Each aliquot will be followed by 1 minute of ventilation.
- 2. Quarter-dose administered with the patient supine and positioned 45° to the left. Each aliquot will be followed by 1 minute of ventilation.
- 3. Quarter-dose administered with the patient supine and positioned 45° to the right. Each aliquot will be followed by 1 minute of ventilation.
- 4. Quarter-dose administered with the patient supine and positioned 45° to the left. Each aliquot will be followed by 1 minute of ventilation.

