During the administration of the lucinactant, the investigator should monitor the patient's oxygen saturation by pulse-oximetry. If the subject does not tolerate one of the 40 ml quarter doses, the dosing for that dose may be terminated at that time. It is recommended that the other quarter doses remain 40 ml; however, a lower dose may be administered for the remaining aliquots at the Investigator's discretion. The investigator will remain with the patient during the first 10 minutes post-treatment. No ventilator changes are to be made during this 10-minute period unless cyanosis or bradycardia occur. At the end of this 10-minute period, the patient's FiO₂ should be weaned to the patient's pre-treatment FiO₂. The patient should not be suctioned for one hour following dosing.

If, in the opinion of the investigator, the patient experiences clinically significant desaturations, hypoxia and/or bradycardia, the lucinactant administration should be temporally suspended to allow the patient to recovery. If the patient doesn't not recovery in a reasonable time, the administration should be terminated. If the administration procedure is re-started and the patient experiences a second episode of clinically significant desaturation, hypoxia and/or bradycardia, the lucinactant administration should be immediately terminated.

Retreatment Doses

Up to 3 retreatment doses are allowed no sooner than 6 hours apart (from completion of previous dose). Subjects are eligible for retreatments if they remain on MV, there is no evidence of pneumothorax, the P/F ratio is under 300 (or S/F ratio is under 315 (43), if no arterial line is present), and there are no safety concerns that would prevent retreatment (in the opinion of the investigator). Retreatments are given at the discretion of the investigator, but it is encouraged that retreatments be given at the recommended time interval if the patient is still receiving MV and meets all retreatment criteria.

Retreatment should be performed in the same manner as the initial treatment.

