### **5.3.2 AEs Related to Surfactant Administration (AEs of Special Interest)**

Individual air leaks (eg, pneumothorax, pulmonary interstitial emphysema, pneumo-mediastinum, pneumopericardium, and subcutaneous emphysema) will be identified by medical review of all AEs and summarized by treatment group.

Occurrences of apnea, bradycardia, and desaturation after the peri-dosing period will be summarized by treatment group.

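### Solicited recording of peri-dosing events ends with dosing, before FiO₂ is weaned, and the SAP never says when the peri-dosing period ends

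*Protocol*

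**What the plan says.** Protocol 8.3.1.2, on tolerability, introduces its four events with "During dosing, the incidence of the following will be recorded". The events are oxygen desaturation, bradycardia, hypotension and ET tube obstruction. No interval after dosing is given.

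Protocol 2.4.1 names transient hypoxemia, bradycardia and hypotension as known risks of instillation and adds: "These are usually not severe, are transient, and typically resolve within 30 minutes".

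Protocol 6.1.2 sets the sequence around a dose:
- Before dosing: "The ventilator will be set at an FiO₂ of 1.00".
- After dosing: "The investigator will remain with the patient during the first 10 minutes post-treatment", and "No ventilator changes are to be made during this 10-minute period unless cyanosis or bradycardia occur".
- Then: "At the end of this 10-minute period, the patient's FiO₂ should be weaned to the patient's pre-treatment FiO₂".

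The first scheduled gas-exchange record after dosing is at 1 hour, with a window of 0.25 hour either side (Protocol 8.2.1). Vital signs are 12-hourly (Protocol 8.2.2). AEs are collected through Day 30, either volunteered or raised in general, non-directed conversation with the bedside staff (Protocol 8.4.5).

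SAP 5.3.1 summarises peri-dosing events. SAP 5.3.2 adds: "Occurrences of apnea, bradycardia, and desaturation after the peri-dosing period will be summarized by treatment group". Neither document says when the peri-dosing period ends.

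**The concern.** Safety and tolerability is a primary endpoint of this single-arm study, and peri-dosing events are the named risk of the procedure. The protocol treats the minutes after dosing as a risk period, since the investigator stays at the bedside, yet it solicits no events then. Any desaturation held off by FiO₂ 1.00 would show once oxygen is reduced, after solicited recording has closed.

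The same event is therefore actively sought if it starts during an aliquot, but left to general AE reporting if it starts at the wean. Protocol 8.4.3.2 also advises that events common in this population should generally not be called related. That could apply to a transient desaturation in a ventilated COVID-19 patient.

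The SAP boundary cannot be applied consistently. Two sites, or two programmers, could place the same event on different sides of it. Post-dose hypotension has no dedicated summary at all. With at most 30 subjects, moving a few events between tables visibly changes a rate. Up to three retreatments repeat the gap.

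**Working it through.** The documents give no event rate, desaturation threshold or sample-size calculation bearing on this, so there is no figure to reproduce. The check is a timeline, a comparison of lists, and two labelled illustrations.

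**1. Timeline**
- Minimum dosing time (Protocol 6.1.2): 4 quarter-doses × 2 aliquots × 1 minute of ventilation = 8 minutes, plus instillation and positioning.
- Wean starts 10 minutes after treatment (Protocol 6.1.2).
- Earliest first gas-exchange record (Protocol 8.2.1): 60 − 15 = 45 minutes. Latest: 60 + 15 = 75 minutes.
- An event starting at the wean and lasting the 30 minutes of Protocol 2.4.1 ends at 10 + 30 = 40 minutes after dosing.

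If the 1-hour clock starts at the end of dosing, 40 < 45: the event falls outside both solicited recording and every scheduled gas-exchange record. If the clock starts at the first aliquot, the wean begins at 8 + 10 = 18 minutes or later and the event can last to 18 + 30 = 48 minutes or later, so a reading at 45 minutes might catch it. Even then, a single spot reading does not record an event with its onset.

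**2. Event lists**
- Protocol 8.3.1.2: desaturation, bradycardia, hypotension, ET tube obstruction.
- Protocol safety variables (1.1 and Section 3): desaturation, bradycardia, ET reflux, hypotension.
- Protocol 7.1: bradycardia, desaturation, hypotension, pallor, gagging/regurgitation/vomiting.
- SAP 5.3.1: desaturation, bradycardia, ET reflux, hypotension, gagging/regurgitation/vomiting.
- SAP 5.3.2, later period: apnea, bradycardia, desaturation. Hypotension is absent.
- SAP Section 10: Tables 5.1.1 and 5.1.2 cover peri-dosing events. No table is titled for the later period.

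**3. Possible number of events affected (both rates assumed)**

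Let p be the share of subjects with an event (20–40%) and f the share of those events starting after dosing (10–50%). Expected subjects outside a during-dosing count = N × p × f. The chance of at least one is 1 − (1 − pf)^N.
- N = 30 (Protocol 9.2): 30 × 0.20 × 0.10 = 0.6, up to 30 × 0.40 × 0.50 = 6.0. Chance of at least one: 0.455 to 0.999.
- N = 20 (SAP 2.2.3): 20 × 0.20 × 0.10 = 0.4, up to 20 × 0.40 × 0.50 = 4.0. Chance of at least one: 0.332 to 0.988.

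**4. Masking illustration, desaturation only (all inputs assumed)**

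Take a baseline P/F of 150 on FiO₂ 0.6, a desaturation registering at PaO₂ 55 mmHg, and a P/F that does not vary with FiO₂.
- On FiO₂ 1.00, P/F must fall to 55 / 1.00 = 55, a drop of (150 − 55) / 150 = 63%.
- On FiO₂ 0.6, it need only fall to 55 / 0.6 = 92, a drop of (150 − 92) / 150 = 39%.

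Drops between 39% and 63% would then show only after the wean. The band shrinks to nothing as the pre-treatment FiO₂ approaches 1.00.

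**The case against.** A reader might infer that late events drop out of a primary tolerability count. The documents do not support that, for these reasons.

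- No such count is defined. The primary endpoint is safety and tolerability as a whole, and AEs, SAEs, mortality, air leaks and vital signs stand beside peri-dosing events.
- Recording of AEs is mandatory whatever their seriousness or relationship, with times of onset and resolution (Protocol 8.4.5). New clinically relevant findings must be reported as AEs (Protocol 7.1), as must clinically significant vital signs (SAP 5.4.1). SAP 5.3.2 covers later bradycardia and desaturation, and hypotension falls under other TEAEs. The DMC may see all AEs.
- Tables 5.1.1 and 5.1.2 are not shown to draw only on the 8.3.1.2 data. SAP 5.3.1 lists events that 8.3.1.2 does not collect, so under-counting in those tables is not proven.
- Thirty minutes is a duration. Because 8.3.1.2 records incidence, an event starting at the last aliquot is counted however long it lasts.
- Masking is an inference. It concerns desaturation, not bradycardia, hypotension or tube obstruction. A lasting loss of oxygenation would appear in the 1-, 2- and 4-hour records.
- The eCRF guidelines or study manual, which are not available here, may set a window. The protocol's account of the earlier infant AHRF study (2.3) uses peri-dosing to mean during dosing.

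All of this stands, and it limits the point to quality of capture and an undefined boundary. It does not remove the point. Non-directed reporting is weaker than solicited recording, and the 2.3 usage makes it more likely that sites will stop recording when dosing stops.

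**Conclusion.** The point holds in a limited form. As written, solicited capture of the named dosing risks ends with dosing, at least 10 minutes before the wean begins. From then to the 1-hour reading, capture rests on non-directed AE reporting. The events remain reportable through Day 30, but are captured less reliably and summarised elsewhere. Separately, the boundary between SAP 5.3.1 and 5.3.2 is undefined, hypotension is missing from the later summary, and the event lists disagree.

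The size cannot be estimated from the documents. The illustration of 0.6 to 6.0 subjects of 30, or 0.4 to 4.0 of 20, rests wholly on assumed rates and counts events outside a during-dosing tally, not events lost to the trial. The timeline result (40 against 45 minutes) depends on the 1-hour clock starting at the end of dosing. This is a cheap improvement to the recording rule and does not invalidate the safety assessment.

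**What to change.** - In Protocol 8.3.1.2, replace the during-dosing limit with a bounded window for each treatment and retreatment: from the first aliquot until 30 minutes after the last aliquot, or until FiO₂ is back at its pre-treatment value if that is later, but no later than 60 minutes after the last aliquot. The cap matters: without it, a worsening patient whose FiO₂ never returns would have disease progression counted as peri-dosing. At 60 minutes the window also closes well before the earliest retreatment, 6 hours after the previous dose.
- Record onset time, so that events beginning during and after dosing can be shown separately, and the FiO₂ at any desaturation.
- Use the same window to define peri-dosing in SAP 5.3.1, SAP 5.3.2 and Tables 5.1.1 and 5.1.2.
- Align the event lists across Protocol 8.3.1.2, the safety variables, Protocol 7.1 and SAP 5.3.1, and add hypotension to SAP 5.3.2.

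This changes recording only, not dosing, ventilation or any other care. The cost is an eCRF page, short text changes in both documents and a longer bedside recording period. Pulse oximetry is already monitored during administration and an arterial line is an entry criterion. The reported peri-dosing rate will be somewhat higher, and part of the increase will reflect underlying disease. The onset time helps readers to judge how much.
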